## 1. INTRODUCTION

This statistical analysis plan (SAP) describes the statistical analysis methods and data presentations to be used in tables, figures, and listings (TFLs) in the clinical study report (CSR) for Study GS-US-417-4048. This SAP is based on Protocol GS-US-417-4048 dated 12 January 2017 and the electronic case report form (eCRF). The SAP will be finalized before database finalization. Any changes made after the finalization of the SAP will be documented in the CSR.

### 1.1. Study Objectives

The primary objective of this study is as follows:

- To evaluate the pharmacokinetic (PK) of filgotinib and its metabolite, GS-829845 (formerly G254445), in subjects with impaired hepatic function relative to matched, healthy controls

The secondary objective of this study is as follows:

- To evaluate the safety and tolerability of filgotinib in subjects with normal and impaired hepatic function

### 1.2. Study Endpoints

The primary endpoints are PK parameters  $AUC_{last}$ ,  $AUC_{inf}$ , and  $C_{max}$  for filgotinib and GS-829845.

The secondary endpoints include the incidence of adverse events (AEs), laboratory abnormalities, vital sign changes and safety ECG abnormalities.

### 1.3. Study Design

Study GS-US-417-4048 is an open-label, adaptive, single-dose Phase 1 study to evaluate the PK of filgotinib in subjects with impaired hepatic function. Up to 3 cohorts of subjects with hepatic impairment and their matched healthy controls are expected to enroll in this study.

- Cohort 1 (Moderate Hepatic Impairment): 20 subjects (10 subjects with moderate hepatic impairment and 10 healthy matched controls for 8 evaluable subjects per group).
- Adaptive Cohort 2 (Severe Hepatic Impairment): 20 subjects (10 subjects with severe hepatic impairment and 10 healthy matched controls for 8 evaluable subjects per group).
- Adaptive Cohort 3 (Mild Hepatic Impairment): 20 subjects (10 with mild hepatic impairment and 10 matched healthy controls for 8 evaluable subjects per group).

The extent of impairment is based on Child-Pugh-Turcotte (CPT) classification system. Class B in CPT system indicates moderate hepatic impairment for this study.

A subject with normal hepatic function may serve as a matched control across cohorts but may only serve as a matched control to one hepatic impaired subject within a cohort.

Subjects in adaptive Cohort 2 (Severe Hepatic Impairment) and Cohort 3 (Mild Hepatic Impairment) may be enrolled after the review of safety and PK data from subjects in Cohort 1 (Moderate Hepatic Impairment).

Following completion of Screening and Day -1 assessments, eligible subjects will be confined to the study center beginning Day -1 (one day before dosing) until the completion of assessments on Day 6. Subjects will return for an in-clinic follow-up (FU) visit on Day 15 ( $\pm$  1 day).

A single dose of 100 mg filgotinib (1 x 100 mg tablet) will be administered in a fasted state on Day 1.

### **Pharmacokinetic Assessments**

Intensive PK sampling will occur relative to dosing of filgotinib at the following time points:

Day 1: 0 (predose,  $\leq$  5 minutes prior to dosing), 0.5, 1, 2, 3, 4, 5, 6, 8, 12, 18, 24, 36, 48, 72, 96, and 120 hours postdose

A blood sample for PK analysis will be collected at the Early Termination (ET) visit (if applicable) and may be analyzed.

### **Protein Binding Assessment**

Protein binding of filgotinib and GS-829845 will be assessed at or near their  $T_{max}$  timepoints as well as at another later time point.

### **Safety Assessments**

Safety will be evaluated by assessment of clinical laboratory tests, physical examinations including vital signs at various time points during the study, ECGs at designated time points, and by documentation of AEs.

Assessment of AEs and concomitant medications will continue throughout the study for all subjects.

- Complete physical exam: Screening, the FU visit or the ET visit (if applicable)
- Symptom driven physical exam: Days -1, 1, and every day during confinement
- Vital signs (blood pressure, heart rate, respiration rate, and body temperature): Screening, Days -1, 1, 3, 6, at the FU visit or the ET visit (if applicable)
- Height: Screening

- Weight: Screening and Day -1
- Clinical laboratory tests (hematology, blood chemistry, and urinalysis): Screening, Days -1, 1, 6 and the FU visit or the ET visit (if applicable)
- Urine drug, cotinine, and alcohol assessments: Screening, Day -1, and the FU visit or the ET visit (if applicable)
- 12-lead Electrocardiogram (ECG): Screening, Days -1, 1, 6, and the FU visit or the ET visit (if applicable)
- Serum Pregnancy Test (women of childbearing potential only): Screening, Days -1, 6, and the FU visit or the ET visit (if applicable)
- Serology Test (HBV, HCV[Ab; if positive, then reflex HCV RNA], HIV-1/2): Screening
- $\alpha$ -fetoprotein Test: Screening

#### **1.4. Sample Size and Power**

With 16 (8 per group) evaluable subjects, the estimated two-sided 90% CI of the geometric least-square mean (GLSM) ratio of test vs reference groups, with regards to PK parameters (AUC and  $C_{max}$ ) would be within (50%, 200%) with over 95% probability, if the estimated GLSM ratio were 1.0. This is assuming the SDs for PK parameters between subjects within each group is no more than 0.347 (or 0.203) for the natural logarithm-transformed PK parameters for filgotinib (or GS-829845). Such assumptions are supported by PK data from a prior Gilead study of filgotinib (GS-US-417-3900) with 100 mg dose in healthy volunteers.

An overage of 2 subjects per group will be enrolled in order to accommodate subject drop-outs, so a total sample size of 20 subjects (10 per group) for each cohort will be required.

## **2. TYPE OF PLANNED ANALYSIS**

### **2.1. Data Monitoring Committee Analyses**

This study does not have a data monitoring committee (DMC). Therefore, no analyses will be conducted for the DMC.

### **2.2. Interim Analysis**

No interim analysis is planned.

### **2.3. Final Analysis**

After all subjects have completed the study, outstanding data queries have been resolved or adjudicated as unresolvable, and the data have been cleaned and finalized, the final analysis of the data will be performed.

### **2.4. Changes from Protocol-Specified Analysis**

No changes from protocol-specified analyses are planned.

### **3. GENERAL CONSIDERATIONS FOR DATA ANALYSES**

Analysis results will be presented using descriptive statistics. For categorical variables, the number and percentage of subjects in each category will be presented; for continuous variables, the number of subjects (n), mean, standard deviation (SD) or standard error (SE), median, first quartile (Q1), third quartile (Q3), minimum, and maximum will be presented.

By-subject listings will be presented for all subjects in the All Enrolled Analysis Set, and sorted by subject identification (ID) number in ascending order, visit date, and time (if applicable), unless otherwise specified. Data collected on log forms, such as AEs, will be presented in chronological order within subject. Age, sex at birth, race, and ethnicity will be included in the listings, as space permits.

#### **3.1. Analysis Sets**

Analysis sets define the subjects to be included in an analysis. Analysis sets and their definitions are provided in this section. The analysis set will be identified and included as a subtitle of each table, figure, and listing.

For each analysis set, the number and percentage of subjects eligible for inclusion will be provided in the disposition table as detailed in Section 4.

##### **3.1.1. All Enrolled Analysis Set**

The All Enrolled Analysis Set includes all subjects who received a study subject ID number in the study after screening.

This is the primary analysis set for safety listings.

##### **3.1.2. Safety Analysis Set**

The Safety Analysis Set includes all subjects who took study drug. This is the primary analysis set for safety tables.

##### **3.1.3. Pharmacokinetic Analysis Sets**

The PK Analysis Sets include all enrolled subjects who took study drug and have at least 1 nonmissing postdose concentration value reported by the PK laboratory for the corresponding analytes. These are the primary analysis sets for all PK analyses.

#### **3.2. Strata and Covariates**

This study does not use a stratified randomization schedule in enrolling subjects. No covariates will be included in the analyses.

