Based on PK properties of filgotinib, the “reduced PK study design” is considered appropriate following the FDA Guidance. In humans, filgotinib is highly metabolized to its active metabolite GS-829845, primarily by carboxylesterase isoform 2 (CES2) in the intestine and to a lesser extent by CES1 in the liver. Following a single dose of [¹⁴C]-filgotinib, a majority of the dose (86.9%) was recovered in urine, suggesting that renal clearance is the main pathway of elimination for filgotinib and its metabolites. GS-829845 (54.0% of the dose) and its *N*-glucuronide derivative (14.6% of the dose) were the major species excreted in urine, followed by the parent filgotinib (9.37% of the dose). Among the 15.4% radioactivity recovered in feces, GS-829845 and filgotinib accounted for 8.88% and 4.47% of dose, respectively. Based on these data, significant changes in plasma exposures of filgotinib or GS-829845 are not expected with impairment in hepatic function. Therefore, it is considered safe to evaluate a single dose of 100 mg filgotinib in subjects with moderate hepatic impairment first, followed by subjects with mild or severe hepatic impairment in an adaptive manner, if indicated.

Finally, the data from this study will inform dosing recommendations for subjects with chronic inflammatory disease including RA, UC, or CD who have hepatic dysfunction.

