8.7. Pharmacokinetic Analysis

Plasma concentrations over sampling time and PK parameters (C_{max} , T_{max} , C_{last} , T_{last} , λ_z , AUC_{last} , AUC_{inf} , $\%AUC_{exp}$, $t_{1/2}$, CL/F , and V_z/F , as appropriate) for filgotinib and GS-829845 will be listed and summarized by hepatic function group using descriptive statistics (eg, sample size, mean, SD, $\%CV$, median, first quartile, third quartile, minimum, and maximum).

An analysis of variance appropriate for a parallel design will be fitted to the natural logarithmic transformation of PK parameters (AUC_{last} , AUC_{inf} , and C_{max}) for filgotinib and GS-829845. Two-sided 90% CIs will be calculated for the GLSM ratios of PK parameters between hepatic impairment group versus the matched control (normal hepatic function) group. If the 2-sided 90% CIs of the GLSM ratio for AUC_{last} , AUC_{inf} , and C_{max} of filgotinib or GS-829845 falls within the [50%, 200%] bound, the null hypothesis that subjects with hepatic impairment exhibit PK parameter change of at least 2-fold for filgotinib or GS-829845 compared with subjects with normal liver function will be rejected.

Protein binding of filgotinib and GS-829845 at their T_{max} and another later time point will be summarized by hepatic function group using descriptive statistics. Unbound PK parameters such as CL_u/F , and V_{zu}/F will be calculated as appropriate and summarized by hepatic function group. Relationships between measures of hepatic function (ie, CPT score, serum albumin, total bilirubin, prothrombin time, and International Normalized Ratio [INR]) and primary filgotinib/GS-829845 PK parameters will be evaluated.

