**Table 8-3. Statistical Comparisons for Pharmacokinetic Analyses**

Analyte	Parameter	Comparison	
		Test	Reference
Filgotinib	AUC last	Moderately impaired hepatic function	Normal hepatic function
	AUC inf		
	C max		
	AUC last	Severely impaired hepatic function	Normal hepatic function
	AUC inf		
	C max		
	AUC last	Mildly impaired hepatic function	Normal hepatic function
	AUC inf		
	C max		
GS-829845	AUC last	Moderately impaired hepatic function	Normal hepatic function
	AUC inf		
	C max		
	AUC last	Severely impaired hepatic function	Normal hepatic function
	AUC inf		
	C max		
	AUC last	Mildly impaired hepatic function	Normal hepatic function
	AUC inf		
	C max		

For each analyte and each PK parameter, a parametric (normal theory) analysis of variance (ANOVA) model will be fitted to the natural log-transformed values of the PK parameter under evaluation.

The statistical model will include hepatic function group as a fixed effect.

The following SAS® PROC MIXED code will provide the comparison between the hepatic function groups and the 90% CI calculations for natural log-transformed PK parameters.

```
proc mixed;  
  by analyte paramcd;  
  class subjid hepaticgrp;  
  model lnest = hepaticgrp / ddfm = kr;  
  repeated / group = hepaticgrp  
  lsmeans hepaticgrp / e diff cl alpha = 0.1;  
  estimate 'Impaired versus Normal' hepaticgrp 1 -1 / cl alpha = 0.10;  
  ods output Estimates = LS_Diffs LSMeans = LS_Means CovParms = MSE;  
run;
```

The ESTIMATE statement will be used to produce the point estimate and the corresponding 90% CI of the difference in PK parameters of interest on a logarithmic scale. The test-to-reference ratio and associated 90% CI will be calculated by taking the exponential of the point estimate and the corresponding lower and upper limits, which is consistent with the two one-sided tests approach {[U.S. Department of Health and Human Services Food and Drug Administration Center for Drug Evaluation and Research \(CDER\) 2001](#), [U.S. Department of Health and Human Services Food and Drug Administration Center for Drug Evaluation and Research \(CDER\) 2003](#)}.

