Nonparametric analyses for the PK parameters CL/F, Vz/F, and  $t_{1/2}$ , are routinely performed. When needed, these analyses can be performed using the Wilcoxon rank sum test for parallel design between the test and reference groups for filgotinib and GS-829845.

```
proc npar1way data=param wilcoxon;  
  class hepaticgrp;  
  var aval;  
run;
```

To evaluate the protein binding of filgotinib and GS-829845, the percent of unbound filgotinib and GS-829845 at  $T_{max}$  and a later time point will be summarized by time point and hepatic function group. Protein binding data for individual subject will be presented in a listing.

For subjects with hepatic impairment, the relationship between plasma PK exposure parameters ( $AUC_{last}$ ,  $AUC_{inf}$  and  $C_{max}$ ) and overall CPT impairment score may be explored using Spearman correlation analysis and examined graphically. The relationship between the PK parameters

( $AUC_{last}$ ,  $AUC_{inf}$  and  $C_{max}$ ) and baseline lab tests (albumin, total bilirubin, prothrombin time, and International Normalized Ratio [INR]) will be also explored using Spearman correlation analysis and examined graphically for hepatic impaired subjects and for all subjects by hepatic function group.

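### Does the absence of a planned creatinine-clearance adjustment for GS-829845 leave the hepatic comparison unsound?

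*SAP*

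**What the plan says.** SAP 3.2 states: "No covariates will be included in the analyses". SAP 8.1.3.2 fits an ANOVA to each log-transformed PK parameter: "The statistical model will include hepatic function group as a fixed effect". The accompanying code gives each group its own variance ("repeated / group = hepaticgrp").

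The exploratory exposure relationships in Protocol 8.7 and SAP 8.1.3.2 involve hepatic measures only: CPT score, albumin, total bilirubin, prothrombin time and INR. CLcr is not among them.

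CLcr appears in two places. It must be at least 60 mL/min for every subject (Protocol 4.2.1, inclusion 5), and it is summarised by hepatic function group and listed by subject (SAP 5.2).

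On elimination, Protocol 1.3 says that "renal clearance is the main pathway of elimination for filgotinib and its metabolites". It reports 54.0% of the dose in urine as GS-829845, 14.6% as its N-glucuronide and 9.37% as parent, with 8.88% in feces as GS-829845.

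The only decision rule is in Protocol 8.7: the two-sided 90% CI of the ratio must lie within 50% to 200%.

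**The concern.** The comparison is not randomised, and matching leaves out the organ function that the protocol names as the main route of elimination. If impaired subjects had lower CLcr than their controls, GS-829845 (a primary analyte) would accumulate for a renal reason, and the group-only model would attribute the difference to hepatic impairment. With covariates ruled out and CLcr missing from the correlations, any adjustment would be chosen after the data were seen. The study is meant to inform dosing recommendations, so a misattributed difference could matter.

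**Working it through.** **The plan's own figure.** Inputs from SAP 1.4: 8 evaluable per group and log-scale SD 0.347 (filgotinib) or 0.203 (GS-829845). With a true ratio of 1.0 and a 90% t-interval on 14 df, one million simulated trials put the CI within 50% to 200% in 96.8% (SD 0.347) and more than 99.9% (SD 0.203). The stated figure of over 95% is reproduced.

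**Effect of a renal imbalance.** Assume no hepatic effect and AUC inversely proportional to clearance. Let f be the renal share of GS-829845 elimination and r the impaired/control CLcr ratio. Then

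AUC ratio = 1 / ((1 − f) + f·r).

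The documents do not give f directly. Values from the Protocol 1.3 recoveries:
- 0.54, the share of dose;
- 54.0/(54.0 + 14.6 + 8.88) = 0.70;
- 54.0/(54.0 + 14.6) = 0.79, leaving out fecal GS-829845.

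The documents give no r, so it is varied. The CI half-width on the log scale is 1.761 × 0.203 × √(2/8) = 0.179, a factor of 1.196.

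| r | AUC ratio (f = 0.54, 0.70, 0.79) | Expected upper 90% limit | Chance CI is within 50–200% |
|---|---|---|---|
| 0.9 | 1.06, 1.08, 1.09 | 1.26, 1.29, 1.30 | above 99.9% |
| 0.8 | 1.12, 1.16, 1.19 | 1.34, 1.39, 1.42 | above 99.9% |
| 0.7 | 1.19, 1.26, 1.31 | 1.43, 1.51, 1.57 | 99.9%, 99.6%, 99.0% |

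Counting the glucuronide as renal elimination as well gives f = 68.6/77.48 = 0.89. At r = 0.7 the ratio is then 1.36 and the chance is 97%. With the larger filgotinib SD (factor 1.357), the expected upper limit at ratio 1.31 is 1.31 × 1.357 = 1.78, still below 2.

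Filgotinib itself barely moves: f = 0.0937 gives 1.02 at r = 0.8 and 1.03 at r = 0.7.

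**What would break the criterion.** The expected upper limit reaches 2 at a ratio of 2/1.196 = 1.67. That needs r = 0.26, 0.42 or 0.49 for the three shares. No subject may be below 60 mL/min, so the control mean would have to be at least 60/0.489 = 123 mL/min with every impaired subject at the floor. For f = 0.89 the figures are r = 0.55 and 60/0.546 = 110 mL/min.

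**How large r could plausibly be.** Cockcroft-Gault depends on age, sex, weight and creatinine. If every impaired subject were a full 10 years older than the control (65 against 55), the age term would give (140 − 65)/(140 − 55) = 75/85 = 0.88 and an AUC ratio of 1.07 to 1.10. With age, sex and weight equal, r = 0.8 needs mean creatinine 1/0.8 = 1.25 times that of controls, and r = 0.7 needs 1.43 times. Clinically significant renal disorders (exclusions 10 and 25) and hepatorenal syndrome (exclusion 18) are excluded.

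**What adjustment would buy.** Take an SD of ln(CLcr) of 0.20 (assumed), f of 0.54 to 0.70 and r of 0.8 to 0.7:
- With CLcr measured exactly, the unadjusted ratios of 1.12 to 1.26 become 1.00.
- With CLcr overstated by 20% in impaired subjects, the adjusted ratios are still 1.09 to 1.13. Overstatement is possible because the formula uses actual body weight and ascites is part of the CPT score.
- If CLcr explains nothing, the adjusted CI is wider by (1.771/1.761) × √(1 + (D²/14)/(2/8)) under pooled variance, where D is the imbalance in SDs. This gives 1.14 at D = 1 and 1.39 at D = 1.78 (r = 0.7). With group-specific variances, simulation gives 1.13 and 1.33.
- A Spearman correlation in a group of 8 would reach 5% significance in only 22% to 39% of trials.

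**The case for a change.** The best case for the concern is about interpretation. At r = 0.7 the GS-829845 ratio could be 1.19 to 1.31 with no hepatic effect at all, and no planned estimate would separate a renal from a hepatic cause. The 90% CI would exclude 1 in 51% to 81% of trials (29% to 48% at r = 0.8), against 10% nominal. Specifying one supportive model in advance would cost a few lines, and choosing it afterwards is weaker.

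Three things stand. Neither document plans a CLcr analysis of exposure. The safeguards limit an imbalance without removing it. A later adjustment would be post hoc.

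The rest carries less weight. Excluding 1 is not a criterion in either document. The ratios of 0.7 and 0.8 have no source in them. Group summaries and subject listings would show an imbalance beside the individual PK parameters, and SAP 1 requires changes made after finalisation to be documented in the study report.

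Nor is adjustment clearly the better analysis. The objective compares impaired subjects with matched healthy controls. If mild renal decline accompanies liver disease, it is part of the exposure difference those patients have, and adjusting would remove some of the effect being estimated.

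**Conclusion.** The concern does not hold as an error. The omission is factual, but the group-only model answers the stated objective, and its conclusion on the 50% to 200% criterion withstands a CLcr ratio as low as 0.7. The chance of meeting the criterion is then about 99% or more for renal shares up to 0.79, and 97% at 0.89. At the more plausible ratios near 0.9, the shift in GS-829845 AUC is about 6% to 10%, taken over shares of 0.54 to 0.89.

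This rests on assumed renal shares, on AUC inversely proportional to clearance, and on the SAP's SD of 0.203, which comes from healthy volunteers. A true hepatic effect would add to any renal one, so these figures describe the renal contribution alone. The documents do not show whether a GS-829845 difference of this size would affect dosing. Protocol 1.2.2 puts the metabolite at 10- to 20-fold less potent than the parent.

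Adding CLcr to the exploratory plots would do no harm, but that is a matter of preference. The plan needs no correction here.

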### **3.3. Examination of Subject Subsets**

There are no prespecified subject subsets for analyses.

### **3.4. Multiple Comparisons**

All endpoint tests will be done at the significance level of 0.05 with no multiplicity adjustments.

### **3.5. Missing Data and Outliers**

#### **3.5.1. Missing Data**

In general, missing data will not be imputed unless methods for handling missing data are specified.

The handling of missing or incomplete dates for AE onset is described in Section [7.1.6.2](#).

#### **3.5.2. Outliers**

Outliers of non-PK data will be identified during the data management and data analysis process, but no sensitivity analyses will be conducted. All data will be included in the data analysis.

### **3.6. Data Handling Conventions and Transformations**

In general, age (in years) on the date of the first dose of study drug will be used for analyses and presentation in listings. If an enrolled subject was not dosed with any study drug, the randomization date will be used instead of the first dosing date of study drug. If only the birth year is collected on the CRF, “01 July” will be used for the unknown birth day and month for the purpose of age calculation. If only birth year and month are collected, “01” will be used for the unknown birth day.

Non-PK data that are continuous in nature but are less than the lower limit of quantitation (LOQ) or above the upper LOQ will be imputed as follows:

- A value that is 1 unit less than the LOQ will be used to calculate descriptive statistics if the datum is reported in the form of “< x” (where x is considered the LOQ). For example, if the values are reported as < 50 and < 5.0, values of 49 and 4.9, respectively, will be used to calculate summary statistics. An exception to this rule is any value reported as < 1 or <0.1, etc. For values reported as < 1 or < 0.1, a value of 0.9 or 0.09, respectively, will be used to calculate summary statistics.
- A value that is 1 unit above the LOQ will be used to calculate descriptive statistics if the datum is reported in the form of “> x” (where x is considered the LOQ). Values with decimal points will follow the same logic as the bullet point above.
- The LOQ will be used to calculate descriptive statistics if the datum is reported in the form of “≤ x” or “≥ x” (where x is considered the LOQ).

If methods based on the assumption that the data are normally distributed are not adequate, analyses may be performed on transformed data or nonparametric analysis methods may be used, as appropriate.

Natural logarithmic transformation will be used for analyzing concentrations and PK parameters. Concentration values that are below the limit of quantitation (BLQ) will be presented as “BLQ” in the concentration data listing. Values that are BLQ will be treated as 0 at predose time points, and one-half the value of the lower limit of quantitation (LLOQ) at postdose time points for determination of summary and order statistics.

The following conventions will be used for the presentation of summary and order statistics:

- If at least 1 subject has a concentration value of BLQ for the time point, the minimum value will be displayed as “BLQ.”
- If more than 25% of the subjects have a concentration data value of BLQ for a given time point, the minimum and Q1 values will be displayed as “BLQ.”
- If more than 50% of the subjects have a concentration data value of BLQ for a given time point, the minimum, Q1, and median values will be displayed as “BLQ.”
- If more than 75% of the subjects have a concentration data value of BLQ for a given time point, the minimum, Q1, median, and Q3 values will be displayed as “BLQ.”
- If all subjects have concentration data values of BLQ for a given time point, all order statistics (minimum, Q1, median, Q3, and maximum) and summary statistics will be displayed as “BLQ.”

Pharmacokinetic parameters that are BLQ will be imputed as one-half LOQ before log transformation or statistical model fitting.

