## 8. PHARMACOKINETIC EVALUATION/ANALYSIS

### 8.1.1. Estimation of Pharmacokinetic Parameters

Pharmacokinetic parameters will be estimated using Phoenix WinNonlin® software using standard noncompartmental methods. The linear/log trapezoidal rule will be used in conjunction with the appropriate noncompartmental model, with input values for dose level, dosing time, plasma concentration, and corresponding real-time values, based on drug dosing times whenever possible.

All predose sample times before time-zero will be converted to zero.

For area under the curve (AUC), samples below the LLOQ of the bioanalytical assays occurring prior to the achievement of the first quantifiable concentration will be assigned a concentration value of zero to prevent overestimation of the initial AUC. Samples that are BLQ at all other time points will be treated as missing data in WinNonlin. The nominal time point for a dosing interval ( $\tau$ ) may be used to permit direct calculation of AUC over specific time intervals. The appropriateness of this approach will be assessed by the PK scientist on a profile-by-profile basis.

Pharmacokinetic parameters such as  $AUC_{inf}$ ,  $\lambda_z$  and  $t_{1/2}$  are dependent on an accurate estimation of the terminal elimination phase of the drug. The appropriateness of calculating these parameters will be evaluated upon inspection of PK data on a profile-by-profile basis by the PK scientist.

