### 8.1.3. Statistical Analysis Methods

#### 8.1.3.1. General Considerations

Individual subject concentration data and individual subject PK parameters including percentage of protein binding for filgotinib and GS-829845 will be listed and summarized using descriptive statistics by hepatic function group. Summary statistics (numbers of subjects, mean, SD, coefficient of variation, median, minimum, maximum, Q1, and Q3) will be presented for both individual subject concentration data by time point and individual subject PK parameters by treatment. Moreover, the geometric mean, 95% CI, and the mean and SD of the natural log-transformed values will be presented for individual subject PK parameter data.

Individual concentration data listings and summaries will include all subjects with concentration data. The sample size for each time point will be based on the number of subjects with nonmissing concentration data at that time point. The number of subjects with concentration BLQ will be presented for each time point. For summary statistics, BLQ values will be treated as zero at predose and one-half of the LLOQ for postdose time points.

Individual PK parameter data listings and summaries will include all subjects for whom PK parameter(s) can be derived. The sample size for each PK parameter will be based on the number of subjects with nonmissing data for that PK parameter.

The following tables will be provided for each analyte by hepatic function group:

- Individual subject concentration data and summary statistics
- Individual subject PK parameters and summary statistics

The following figures will be provided for each analyte by hepatic function group:

- Individual subject concentration data versus time (on linear and semilogarithmic scales)
- Mean ( $\pm$  SD) concentration data versus time (on linear and semilogarithmic scales)
- Median (Q1, Q3) concentration data versus time (on linear and semilogarithmic scales)

Individual, mean, and median postdose concentration values that are  $\leq$  LLOQ will not be displayed in the figures and remaining points connected.

The following listings will be provided:

- PK sampling details by subject, including differences in scheduled and actual draw times, and sample age
- Individual data on determination of plasma half-life and corresponding regression correlation coefficient

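### SAP 3.6 replaces a BLQ PK parameter by half the LOQ before modelling, which is dimensionally invalid for AUC and conflicts with the SAP's rule that underivable parameters are not modelled

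*SAP*

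**What the plan says.** SAP 3.6 (Data Handling Conventions and Transformations) ends with the rule at issue: "Pharmacokinetic parameters that are BLQ will be imputed as one-half LOQ before log transformation or statistical model fitting". It is not limited to Cmax, and it reaches the statistical model. By contrast, the half-LLOQ rule for concentrations in the same section, and in Protocol 8.3, serves summary statistics only.

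Other parts of the SAP bear on the same subject:

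- **3.1.3** admits to the PK Analysis Set subjects who "have at least 1 nonmissing postdose concentration value reported by the PK laboratory for the corresponding analytes". It does not require any value to be quantifiable.
- **8.1.1** sets BLQ samples before the first quantifiable concentration to zero. For the rest, "Samples that are BLQ at all other time points will be treated as missing data in WinNonlin".
- **Pharmacokinetic Abbreviations** define AUClast as ending at the last quantifiable concentration, and AUCinf as needing Clast and λz.
- **8.1.2** generates parameters only where they can be derived. Its text on molar ratios gives AUC in h*nmol/L and Cmax in nmol/L.
- **8.1.3.2** models subjects who have data for the parameter in question.
- **8.1.3.1** has a similar sentence, "Individual PK parameter data listings and summaries will include all subjects for whom PK parameter(s) can be derived", but it governs listings and summaries, not the model.
- **8.1.4** makes the analysis of all data in the PK Analysis Sets primary and the outlier analysis secondary.

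**The concern.** There are two faults in the specification.

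**Units.** Throughout the SAP the LOQ of PK data is an assay limit for concentrations. Half of it is a possible stand-in for Cmax, which is a concentration. It is not a possible value of AUClast or AUCinf, which are four of the six primary parameter-by-analyte combinations. Its numerical effect would change with the time unit in which AUC happens to be stored.

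**Conflict.** The SAP does not say when an AUC counts as BLQ, nor which rule prevails. A programmer who follows 3.6 gives an all-BLQ subject a log AUC and models it. A programmer who follows 8.1.1, 8.1.2 and 8.1.3.2 leaves that subject out for the analyte. The two would report different primary results from the same data.

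What is at stake is confined to the unlikely case that such a subject occurs. With 8 or 10 per group, one extreme log value is enough to decide the comparison.

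**Working it through.** **Inputs**

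- From SAP 1.4: 8 evaluable and 10 enrolled per group; SD on the ln scale 0.347 (filgotinib) or 0.203 (GS-829845); bounds 50% to 200%.
- From SAP 8.1.3.2: 90% CI, separate variance per group, Kenward-Roger df. Satterthwaite df are used here as a stand-in.
- From Protocol 1.2.2: mean AUC 1.38 µg·h/mL = 1,380 h*ng/mL at 100 mg once daily in RA subjects. It is used only for scale, as if it were the geometric mean.
- Assumed: LLOQ 0.5 to 5 ng/mL, because the documents do not give it.

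**Step 1. The plan's own figure.** SAP 1.4 states that, "With 16 (8 per group) evaluable subjects", the CI "would be within (50%, 200%) with over 95% probability, if the estimated GLSM ratio were 1.0". With 14 df, t = 1.761 and the half-width is 1.761 × 0.347 × √(2/8) = 0.306, so the expected CI is exp(±0.306) = 0.74 to 1.36. Given an estimated ratio of exactly 1.0, the CI stays inside the bounds if the observed SD is below ln 2 / (1.761 × 0.5) = 0.787, which has probability above 99.9%. With a true ratio of 1.0, the simulated probability is about 97%. The stated figure reproduces.

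**Step 2. One impaired subject imputed.** Let f be the factor by which the imputed value lies below the group's geometric mean, and d = ln f. The other subjects sit at ratio 1.0 with SD s.

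- f = 1,380 / (LLOQ/2)
- Ratio = exp(−d/n)
- Variance of the impaired group = [(n−2)s² + ((n−1)/n)d²] / (n−1)
- SE = √[(that variance + s²)/n]
- 90% CI = exp(−d/n ± t × SE)

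For LLOQ 1 and n = 8: f = 2,760 and d = 7.923. The variance is (6 × 0.1204 + 0.875 × 62.77)/7 = 7.95, against the planned 0.12. SE = √[(7.95 + 0.12)/8] = 1.004, df = 7.2 and t = 1.886.

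| LLOQ (ng/mL) | f | Ratio, n = 8 | 90% CI, n = 8 | Ratio, n = 10 | 90% CI, n = 10 |
|---|---|---|---|---|---|
| 0.5 | 5,520 | 0.34 | 0.04 to 2.66 | 0.42 | 0.09 to 2.09 |
| 1 | 2,760 | 0.37 | 0.06 to 2.47 | 0.45 | 0.10 to 1.97 |
| 5 | 552 | 0.45 | 0.10 to 2.07 | 0.53 | 0.16 to 1.74 |

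In simulations of each row, no trial had its CI inside 50% to 200%. One imputed control would move the ratio the other way by the same factor.

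**Step 3. How far the result depends on the assumed LLOQ.** The expected CI leaves the bounds once the imputed value is about 5.3-fold (n = 8) or 9.0-fold (n = 10) below the geometric mean at SD 0.347. At SD 0.203 the thresholds are 6.3-fold and 10.7-fold. Even an LLOQ of 50 ng/mL gives f = 1,380/25 = 55.

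**Step 4. The unit check.** Take LLOQ 1 and n = 8. With AUC in hours, f = 2,760 and the ratio is 0.37. In minutes, f = 165,600 and the ratio is 0.22. In days, f = 115 and the ratio is 0.55. A valid rule would give one answer.

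**Step 5. The alternative.** If the AUC is left missing, 7 against 8 subjects gives an expected CI of 0.73 to 1.37 and a probability of about 95% of meeting the bounds. With 9 against 10 the probability is about 99%.

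**The case against.** The best defence is that, read as a whole, the SAP never produces a BLQ AUC. AUClast must end at a quantifiable concentration, AUCinf needs Clast and λz, underivable parameters are not generated, and only available values are modelled. On that reading the sentence in 3.6 can apply only to Cmax, where the units are right. This is a sensible reading and probably what a careful analyst would do. But 3.6 does not say so. It names PK parameters in general and model fitting in particular, so the conflict remains.

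The trigger is also remote. Site staff give the dose (Protocol 5.5), and 16 postdose samples are taken (Protocol 6.8). SAP 4.3 allows a deviation to be assessed as grounds for excluding a subject from an analysis set. This stands, and it limits the severity.

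A lost or unabsorbed dose would probably leave both analytes unquantifiable. All six parameters would then be flagged, and the subject could be removed under 8.1.4. That also stands, but 8.1.4 runs only if the PK scientist finds data questionable, and its result is secondary. The primary result would keep the imputed values.

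Finally, the size rests on an assumed LLOQ and on an AUC from RA subjects on once-daily dosing. Step 3 shows that the direction of the conclusion does not depend on either. The exact ratio does.

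**Conclusion.** The sentence in SAP 3.6 should be corrected. For AUClast and AUCinf it is dimensionally invalid, and it contradicts 8.1.1, 8.1.2 and 8.1.3.2. If it were applied to one of 8 impaired subjects, the AUC ratio would be about 0.34 to 0.45 when the true ratio is 1.0. With 10 per group it would be about 0.45 at an LLOQ of 1 ng/mL. The 90% CI would almost surely miss 50% to 200%. These figures assume SD 0.347, AUC about 1,380 h*ng/mL and an LLOQ of 0.5 to 5 ng/mL.

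A reader might infer that the primary comparison is biased or likely to fail. The documents do not support that: the rule acts only if essentially a whole profile is below the LLOQ, and nothing suggests this is expected. A reader might also infer that the imputed value is always thousands of times too low. At an LLOQ of 5 ng/mL the factor is 552. Nor is half the LLOQ wrong for every parameter, since its units fit Cmax.

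**What to change.** Amend SAP 3.6 as follows:

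1. Remove the imputation for AUClast and AUCinf.
2. State that a parameter that cannot be derived is missing for that analyte and is not in its primary ANOVA, in line with 8.1.2 and 8.1.3.2.
3. List any subject with no quantifiable postdose concentration for an analyte, with the reason.
4. If half the LLOQ is to be kept, limit it to Cmax as a sensitivity analysis, and show results with and without the subject.

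The cost is a few lines of SAP text, with no new data or procedures. The downsides are one fewer subject for that analyte and a possible bias if that subject's exposure was truly very low. The listing and the with-and-without results would make that visible.
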